## 6.0 REGISTRATION PROCEDURES

### 6.1 Patient registration

**6.1.1 Pre-registration: Emory:** Pre-registration must be completed and sent to the Central Subject Registrar and to the Office of Clinical Research. After receipt of the pre-registration form and confirmation of a valid, signed informed consent form/HIPAA authorization form, the Winship Clinical Trials office will assign a patient study number.

**Participating site(s):** After each subject signs consent, the Central Subject Registration form is to be completed and sent to Winship Clinical Trial Office within 48 hours of consent. This form, along with the valid, signed informed consent form/HIPAA authorization form, is to be faxed or emailed to Winship's Central Subject Registrar per instructions on the form. The Winship Clinical Trials office will assign a patient study number to these patients.

**6.1.2 Patient study number assignment/confidentiality:** Subjects will be assigned a coded designation according to the site at which the subject signs consent. (QTR01, the site initials, and enrollment number entered on study will be assigned QTR01EM001). Actual names, contact information and relationship to this code will be kept secure in the Winship Clinical Research Office.

**6.1.3 Registration:** Participating site(s): The Eligibility checklist is to be printed from OnCore and verified by 2 people, of which one must be a clinical investigator or co-investigator. The completed and signed eligibility checklist along with all redacted supporting source documentation must be submitted to the Winship Multi-site Coordinator or designee ([contact]) within 14 days after pre-registration but no later than 2 business days from scheduled treatment visit. Eligibility will be confirmed by a clinical principal or co-investigator and the Multi-site Coordinator or designee within 2 business days of receipt of all eligibility documentation and confirmation will be sent to the participating site along with cohort assignment, if subject meets criteria. Once eligibility is confirmed, then patient will be registered and scheduled for appropriate appointments.

**6.2 Investigator registration/requirements:** Prior to recruitment of subjects to this trial,

investigators must complete training as required per institutional IRB for participation on clinical trials along with protocol specific training. Each investigator must be registered (FDA Form 1572 with original signature, current CV, Supplemental Investigator Data Form with signature, and Financial Disclosure Form with original signature) and maintain an “active” registration status.

### 6.3 Site registration/requirements

- 6.3.1 **IRB:** IRB approval for this study will be obtained and maintained for the duration of the study treatment and follow up times. Documentation of initial and continued IRB approval will be submitted to the Winship Clinical Research Office.
- 6.3.2 **Radiation Therapy:** All institutions participating on this trial will need to be credentialed to use IMRT on the study. Previous credentialing for cooperative group and/or consortium trials (eg. RTOG/NRG, ABTC, etc.) is acceptable.
- 6.3.3 **Neurocognitive certification:** All study staff that will be administering neurocognitive testing will need to be certified as specified in section 7.2.1. Previous certification for administering these tests on other studies is acceptable after submission of documentation to the Winship Clinical Research Office.

## 7.0 STUDY EVALUATIONS

### 7.1 Summary of Active Monitoring Schedule

Tests and procedures	Pre-reg	≤21 days prior to start of therapy	Chemoradiation (RT+TMZ, 6 weeks)						Adjuvant TMZ Cycles 1-12  ≤7 days before each cycle	After completion of adjuvant TMZ
			1	2	3	4	5	6		
Path diagnosis	X									
H&P, weight, KPS		X		X 		X 		X 	X	X 
Height		X								
Neuro exam		X		X 		X 		X 	X	X 
Adverse event assessment		X	X 	X 	X 	X 	X 	X 	X	X 
Rad Onc consult	X 									
Neuro Onc consult	X 									
CBC w/diff		X	X 	X 	X 	X 	X 	X 	X	
CMP 		X	X 	X 	X 	X 	X 	X 	X	
MRI w/contrast 		X							X 	X 
sMRI (Research)		X			X 					
Steroid/anti-Sz/chemo med documentation		X	X 	X 	X 	X 	X 	X 	X	
Neurocognitive and QOL assessments (Research)		X							X 	X 
Pregnancy test		X 								

-  Comprehensive Metabolic Panel (CMP) - Sodium, potassium, bicarbonate, chloride, BUN, creatinine, calcium, glucose, total bilirubin, SGOT (AST), SGPT (ALT), alkaline phosphatase, albumin, total protein (Standard care). The frequency of CMP will be up to the treating physician's discretion.
-  Standard diagnostic brain MRI w/ & w/o contrast.
-  Either Rad Onc or Neuro Onc consultation needs to be completed at pre-registration. The other consultation can be completed  $\leq$  21 days before initiation of therapy. (Standard care)
-  To be completed only in women of childbearing potential. Test obtained  $\leq$  21 days prior to registration. May use a test result obtained for other clinically warranted indications if the test date is within the above time window. (Standard care)
-  To be assessed during chemoradiation. (Standard care)
-  Document steroids, anti-seizure, and temozolamide meds weekly during cycle 1. (Standard care)
-  To be performed every other week starting on week 2 of chemoradiation. (Standard care)
-  sMRI should be performed during the 3rd week of chemoradiation (after 10 fractions up to 15 fractions, or prior to receiving the 16th fraction). ([Research](#))
-  TMZ cycles will be determined at treating physician's discretion. (Standard care)
-  Standard diagnostic brain MRI w/ & w/o contrast to be completed  $\leq$  7 days prior to starting each odd number cycles. (Standard care)
-  To be performed every 6 months ( $\pm$  1 month) after pre-cycle 2 assessment until progression (will attempt to obtain final assessment only if date of progression is  $>$  3 months from previous assessment) or until approximately 2 years after pre-cycle 2 assessment (maximum of 4 additional assessments). ([Research activity](#))
-  Follow-ups and standard diagnostic brain MRI w/ & w/o contrast to be completed 1 month ( $\pm$  2 weeks) after completion of adjuvant TMZ chemotherapy and then every 3 months ( $\pm$  2 weeks) (until approximately 2 years after RT). Subsequent followups/MRIs will be determined by treating physician. (Standard care)

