## 11.0 TREATMENT EVALUATION

## 11.1 Objectives – (see section 2.1-3)

## 11.2 Imaging assessment

**11.2.1 Conventional MRI scans (Standard care):** Diagnostic MRI scans with and without contrast will be utilized to assess for response.

**11.2.2 sMRI (Research, 2 scans at week 0 (before treatment) and week 2):** 3-D whole brain MR spectroscopic imaging sequence (EPSI/GRAPPA) and the analysis program MIDAS (Metabolic Imaging Data Analysis System) were developed by [name] (scientific PI of U of Miami) in 2006 [31-42]. The scan will be done in 3T Siemens MR scanner (TIM/TRIO, Prisma, Skyra) or equivalent. Metabolite maps and their ratio maps will be calculated in MIDAS. Due to some degree of variability of Cho/NAA ratio between subjects, we will use the signal from contralateral normal white matter for normalization. We will use a web-based sMRI clinical interface to extract information from MIDAS to visualize the metabolite maps for efficient clinical workflow of the MIDAS results for busy clinicians and non-MRS experts. In addition, this web-based tool allows effective data sharing among imaging scientists and clinicians for consultation and storage of de-identified data sets (this sMRI clinical interface has been used at Emory (NCI U01 CA172027 & NCI R21 NS100244; Emory IRB00055973). sMRI studies will be obtained at the schedule outlined in section 7.1.

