Because of difficulties in the interpretation of pseudo-progression on MRI, the first three post-RT/TMZ scans should NOT be used to declare progression. Progressive worsening on subsequent imaging studies usually distinguishes true progression from pseudoprogression. In particular, DSC perfusion imaging may be helpful at distinguishing true and pseudoprogression. If the rCBV map does not show evidence of increased perfusion in regions with increasing contrast-enhanced lesion(s), then pseudoprogression is favored and patient may be maintained on study. Subsequent increases up to 6 months post-RT will be evaluated on a case-by-case at a multi-disciplinary tumor board of the respective institution to assist in making a determination regarding true versus pseudoprogression and whether pathologic sampling would be beneficial. The date of progression will be backdated to when the changes were first observed in the case that the patient is later determined to have true progression.

**11.3.3.5 Regressive Disease (REGR):** (Evaluable disease only) Unequivocal reduction in extent of contrast as compared to baseline-enhancement or a decrease in mass effect as agreed upon independently by primary physician and quality control physicians; no new lesions.

**11.3.3.6 Unknown:** Progression has not been documented and one or more measurable sites have not been assessed.

**11.4 Best Response:** This will be calculated from the sequence of objective statuses. For patients with all disease sites assessed every evaluation period, the best response will be defined as the best objective status as measured according to section 11.5.

**11.5 Neurological Exam:** Although not used for determining response, it is useful to evaluate improvement in the neurologic exam, as compared with the baseline assessment, that should coincide with objective measurement of tumor size.

NEURO EXAM STATUS (compared to pre-treatment exam)	
Better	Must be on stable or decreasing dose of steroids
Same	Failure to qualify for better or worse
Worse	Include patients requiring increasing steroid doses to remain stable

**11.6 Performance Status:** Patients will be graded according to Karnofsky Performance Status (see Appendix 3).

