### **13.2.2 Procedures to assure data integrity and protocol adherence**

- 13.2.2.1** Imaging and clinical data will be analyzed in a quarterly meeting of investigators, clinical research coordinators and regulatory personnel.
- 13.2.2.2** Adverse event reporting will utilize NCI Common Terminology Criteria for Adverse Events (CTCAE) version 4.0 and is detailed in section 12.0 above.
- 13.2.2.3** Study Team Oversight: The study progress in terms of enrollment, activity of current patients under active treatment, observed toxicities will be reviewed in the monthly Emory Neuro-oncology Working Group. Here there will be random and selected case report form and chart review. Special and problematic items requiring additional attention will be addressed in separate sessions of the Neuro-oncology Working Group occurring up to weekly including selected study investigators, clinical research coordinators and regulatory personnel.
- 13.2.2.4** Training of investigators, clinical research coordinators and regulatory personnel at all sites will be performed by one of the principal investigators utilizing the written protocol and a summary of pertinent treatment activities. Completion of the training of investigators, clinical research coordinators and regulatory personnel will be documented on a study training log.
- 13.2.2.5** External Site Management: Enrollment will occur at Johns Hopkins University and University of Miami
  - Monitoring of Study Activity: Monitoring of study activity will occur by monthly review of enrollment activity of current patients under active treatment, observed toxicities by the investigator, clinical research coordinator and regulatory personnel at Johns Hopkins and University of Miami. The results of this review will be summarized and shared and logged monthly in written form (and verbal form when needed) with the Emory investigators.
  - Investigator Communication: Verbal investigator communication among three sites will occur and be logged quarterly to discuss the content mentioned above.
  - Reporting of Adverse Events Occurring at Johns Hopkins and University of Miami: The criteria and methods of collecting adverse event data outlined in section 12.0 will apply at Johns Hopkins and U of Miami also.

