### 14.3 Exploratory Objectives

14.3.1 To determine whether sMRI-guided, dose-escalated RT increases the overall survival of patients with newly-diagnosed GBMs. Subjects on this study will also be followed for overall survival (OS) which is defined from the time of surgical resection to the time of death. The OS actuarial curve and 1-year OS rate will be assessed and compared to historical controls. The 1-year OS rate of control arm patients on recent trials is approximately 66%

14.3.2 To determine whether sMRI data obtained after initiation of therapy (at 2 weeks after RT/TMZ start and prior to cycle 1 and 5 of adjuvant TMZ) will provide early evidence of GBM progression not seen on standard MRIs. Changes in sMRI parameters over time will be assessed to determine whether they will be able to predict development of recurrence. Global changes in sMRI parameters including to absolute metabolite concentrations or metabolic ratios will be examined to see if these factors may be an early marker of tumor recurrence. In addition, further assessments will be made on a voxel-wise basis to determine whether individual changes may be predictive of ultimate recurrence within particular voxels.

14.3.3 To determine whether performance on neurocognitive and quality-of-life (QOL) assessments in newly-diagnosed GBM patients treated with sMRI-guided, dose-escalated RT differ from historical controls. We will compare performance on neurocognitive and QOL assessments in our 30 subject cohort with performance by historical control cohorts from recent GBM trials (eg. RTOG 0525 and 0825) [45, 46]. Better performance may be attributable to better control of disease while worse performance may imply increased toxicity from the study treatment regimen.

**14.3 Accrual rate and numbers:** The anticipated rate of accrual will be 2-3 patients/month among three sites. This will allow consenting of 30 patients over a period of 1.5 years.

**14.3 Criteria for removal from trial:** All reasons for discontinuation of treatment must be documented.

**14.3.1** Progression of disease will be hard to determine due to pseudoprogression as defined in section 11.3. The final progression free survival will be determined at year 1, which is beyond pseudoprogression possibility.

**14.3.2** Patient may withdraw from study at any time for any reason.

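### Those who call, date and locate progression are not masked to the week-3 sMRI, so a positive answer to exploratory objective 2.3.2 could not be told apart from assessor influence

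*Combined protocol and SAP*

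**What the plan says.** **Predictor.** Section 11.2.2 covers both research scans: "sMRI (Research, 2 scans at week 0 (before treatment) and week 2". Footnote 8 of section 7.1 gives the timing of the second scan only, in the third "week of chemoradiation (after 10 fractions up to 15 fractions, or prior to receiving the" 16th fraction, and is silent on who sees it. Section 14.3.2 states the analysis: "Changes in sMRI parameters over time will be assessed to determine whether they will be able to predict development of recurrence". It adds a voxel-wise version, and section 14.6 repeats the patient-wise and voxel-wise plan.

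**Access.** Section 11.2.2 describes a web interface to "visualize the metabolite maps for efficient clinical workflow of the MIDAS results for busy clinicians and non-MRS experts" and adds that "this web-based tool allows effective data sharing among imaging scientists and clinicians for consultation and storage of de-identified data sets". It makes no distinction between the pre-RT map and the week-3 map. Section 13.2.2.1 says: "Imaging and clinical data will be analyzed in a quarterly meeting of investigators, clinical research coordinators and regulatory personnel".

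**Outcome.** Section 11.2.1 assigns response assessment to diagnostic MRI with and without contrast. Section 11.3.3.4 defines progression by a 50% volume increase, a new lesion, clear clinical worsening, or failure to return because of death or deterioration. Perfusion (rCBV) is the named aid. Increases up to 6 months after RT are to be "evaluated on a case-by-case at a multi-disciplinary tumor board of the respective institution". Once progression is accepted as true, its date is moved back to when the changes were first seen.

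**Masking.** No section masks assessors to sMRI, sets a central read, or requires the progression call to be locked before sMRI is linked to it.

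**The concern.** A study of whether a marker predicts an outcome needs the outcome to be settled without knowledge of the marker. Here three parts of the outcome involve judgement:

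- whether growing enhancement is true progression;
- the date to which progression is moved back;
- for the voxel-wise analysis, where the recurrence lies.

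The protocol itself says that early progression and pseudoprogression look the same on standard MRI (section 1.0) and expects more pseudoprogression than usual (sections 11.3.1 and 11.3.3.4). The background sections also show that the team already regards raised Cho/NAA as marking sites of recurrence. A clinician facing an equivocal scan, with a week-3 rise in Cho/NAA open in the same tool, has an obvious tie-breaker. If it is used, even in some patients, a marker with no predictive value will look predictive. At stake is how a positive finding on objective 2.3.2 can be read.

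**Working it through.** The plan states no sample size, alpha or power for this analysis, so it offers no figure to reproduce. The check has two parts.

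**1. Is the route open in the text?**

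| Step | Where | What it establishes |
|---|---|---|
| Maps reach clinicians | 11.2.2 | Permitted for both scans; outcome readers neither named nor excluded |
| Imaging and clinical data meet | 13.2.2.1 | Quarterly, among investigators |
| Call depends on judgement | 11.3.3.4 | Site tumor board, case by case; date moved back |
| Outcome tested against the map | 14.3.2, 14.6 | By patient and by voxel |
| Barrier between map and call | none | No masking, lock or separate read |

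The route is open. The documents do not say that anyone will use it.

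**2. How large could the effect be?**

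Inputs from the documents:
- n = 30 (section 14.5).
- Probability of progression or death by 1 year = 1 − 0.30 = 0.70, from the historical 1-year PFS of about 30% (section 14.2.1).
- Pseudoprogression of about 30% with standard treatment (section 1.0), giving 0.30 × 30 = 9 ambiguous patients.

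Assumptions, not in the documents: the number m of patients whose call stays ambiguous, and the share q of those calls that follow the map.

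Formula: let e = m/30, and split patients into high and low marker. With a null marker, the chance of a progression call is (1 − eq) × 0.70 + eq in the high group and (1 − eq) × 0.70 in the low group. The spurious risk difference is therefore e × q. For m = 9 and q = 0.5 it is 0.30 × 0.5 = 15 percentage points. For m = 3 and q = 0.5 it is 0.10 × 0.5 = 5 points.

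Simulation: a null normal marker; each followed call is set to progression if the marker is above the median; Mann–Whitney test at two-sided 5%; 6,000 to 12,000 runs per setting.

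| Ambiguous patients m | Share following the map q | Apparent AUC | False-positive rate |
|---|---|---|---|
| any | 0 | 0.50 | about 5% |
| 3 | half | 0.53 | about 6% |
| 3 | all | 0.56 | about 7% |
| 9 | a quarter | about 0.55 | about 6% |
| 9 | half | 0.58–0.59 | about 11% |
| 9 | all | 0.67 | 28–30% |
| 12 | half | 0.61–0.62 | about 16% |
| 12 | all | 0.72 | about 51% |

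A second calculation used a high/low marker, 30% equivocal cases and base progression rates of 40% and 65%. By chi-square it gave 7–8% for a quarter, 12–13% for half and 37–38% for all. Fisher's test gave about 4%, 8% and 27–28%, from a null level of 2.5–3%. The pattern is the same: little inflation when few calls follow the map, and substantial inflation when most do.

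**The case against.** The case on the other side is substantial.

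- **The tool permits sharing; it does not prescribe it.** A reader might infer that the week-3 maps are handed to the people who adjudicate progression. No section says so, and 13.2.2.1 sits under data integrity and protocol adherence, not outcome adjudication. This stands: the defect is a missing safeguard, not a documented practice.
- **sMRI is not part of the progression definition.** A reader might call this incorporation bias. That term requires the index test to belong to the reference standard, and sections 11.2.1 and 11.3.3.4 rest on contrast MRI, clinical status and perfusion. This stands: the risk is unmasked-reader influence. Leaving sMRI out of the criteria does not, however, stop an assessor from seeing the map.
- **The plan has protections against early miscalls.** The first three scans after RT/TMZ may not be used to declare progression. With MRIs before odd cycles and a 4–5 week break, the fourth falls before cycle 7, at about 4 + 24 = 28 to 5 + 24 = 29 weeks. Final PFS is determined at year 1, which the protocol regards as beyond pseudoprogression, and section 15.3 collects follow-up pathology reports. This largely stands and argues for fewer than 9 ambiguous patients. It does not protect the date, which can be moved back into the ambiguous period, or the recurrence contour.
- **Masking would be partial.** The pre-RT Cho/NAA map defines GTV3 (section 8.1.4.4), so treating clinicians know the baseline half of any change score. This stands, and the fix must say so.
- **The objective is exploratory.** A reader might conclude that 2.3.2 cannot be answered at all. The documents do not support that: no test or threshold is attached to it, and possible bias limits interpretation without making the data useless.

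**Conclusion.** The concern holds as a gap in masking. Assessors of progression are not kept from the week-3 sMRI, the plan makes the maps available to clinicians for consultation, and part of the outcome is a judgement. A positive result for section 14.3.2 could therefore not be separated from assessor influence, either by patient or in the location of recurrence.

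The size is not known. It runs from almost nothing (5–7%, with 3 ambiguous patients or a quarter of 9 calls following the map), through about 11% (half of 9), to 28–30% (all of 9). The upper figures need every ambiguous call to follow a scan that is by then about six months old, and nothing in the documents supports that as the expected case. The 9 itself borrows an early pseudoprogression rate that the plan expects to have resolved by year 1. The simulation covers the patient-level call only; the spatial effect was not sized.

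The matter is confined to an exploratory objective. It deserves correction because the correction is cheap now, whereas calls already made unmasked could be repaired only by a masked re-read.

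**What to change.** 1. **Sections 11.2.2 and 13.2.2.1:** restrict week-3 maps in the existing web tool to the imaging scientists. Release them to site clinicians, the tumor board and the quarterly meeting only when the existing site assessors have recorded and locked that patient's progression status and date, and any recurrence contour used in the voxel-wise analysis.
2. **Section 14.3.2:** state that status, date and contour are set on conventional imaging (contrast MRI, with perfusion and pathology as already planned) without sMRI overlay. This follows sections 11.2.1 and 11.3.3.4; the no-overlay condition and the lock are new.
3. **Limitation to report:** the pre-RT map stays available for GTV3 planning, so assessors know the baseline map, and spatial agreement between recurrence and that map is not protected.

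**Cost:** wording, access rights in a tool already in use, and a recorded lock date per patient. If contours for the voxel-wise analysis would not otherwise be drawn before sMRI is opened, that order of work must change. No scan or reader is added. The downside is that clinicians see an investigational on-treatment map later. No decision in the protocol uses that map; section 14.6 mentions adaptive planning only as a possible use.
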